1.4.5 Pharmacokinetic assessments

Blood samples for pharmacokinetic measurements of plasma exenatide concentrations for potential future analysis will be collected within the 30 min prior to the start of the standardized meal, according to the schedule presented in Section 9.1.2 and Section 9.1.3 of Appendix F of the CSP.

2. ANALYSIS SETS

2.1 Definition of analysis sets

2.1.1 All patients analysis set

The All patients analysis set will include all patients who provided written informed consent/assent, as relevant.

2.1.2 Randomized analysis set

The Randomized analysis set will include all randomized patients. Randomized patients will be analyzed in accordance to their planned treatment group.

2.1.3 Intent-to-treat (ITT) analysis set

The ITT analysis set will consist of all randomized patients who receive at least 1 dose of randomized study medication. ITT patients will be analyzed in accordance to their planned treatment group.

2.1.4 Evaluable analysis set

The Evaluable analysis set will consist of all randomized patients who receive at least 1 dose of randomized study medication and have at least 1 baseline and post-baseline HbA1c assessment. Evaluable patients will be analyzed in accordance to their planned treatment group.

2.1.5 Safety analysis set

The Safety analysis set will consist of all patients who received at least one dose of study medication.

All safety analyses on adverse events (AEs), clinical laboratory measurements, physical examination findings, vital signs, and antibodies to exenatide will be based on the safety

analysis set. Patients will be analyzed and presented in accordance to the actual treatment received, regardless of planned treatment assignment. If a patient randomized to the placebo arm receives at least one dose of EQW during the controlled assessment period, their actual arm will be derived as EQW.

2.1.6 Pharmacokinetic (PK) analysis set

The PK analysis set will consist of all patients who receive at least 1 dose of EQW, for whom at least 1 post-dose PK concentration assessment is available, and do not deviate from the CSP in ways that would significantly affect the PK analyses, as determined at the final protocol deviations meeting prior to unblinding of this study. Patients will be presented in accordance to the actual treatment received.

2.1.7 Standardized mixed meal test evaluable analysis set

The analysis set will consist of all ITT patients who provide informed consent/assent, as relevant, for the sub-study and participate in the Standardized Mixed-Meal Test, complete study procedures in compliance with the main CSP and the sub-study and have valid and adequate pharmacodynamic measurements (see CSP Appendix F, Section 10) for data analysis. Patients will be presented in accordance to their planned treatment group.

2.2 Violations and deviations

AstraZeneca use International Conference on Harmonization (ICH) E3 terminology for protocol deviations (PD), which are all important deviations related to study inclusion or exclusion criteria, conduct of the trial, patient management or patient assessment. Deviations and/or other factors that may greatly impact the completeness, accuracy, and/or reliability of the study data or that may significantly affect a patient's rights, safety, or well-being include, at a minimum, the following categories:

- Patients who do not meet the inclusion criteria and/or who meet one or more of the exclusion criteria (eligibility and entry criteria) but enter the study and are potentially randomized and treated.
- Patients who receive the incorrect randomized study medication at any time during the 24-week double-blind treatment period. In addition, patients assigned to the incorrect IVRS randomization stratification factor as compared to HbA1c test result at screening: Screening HbA1c strata ($<9.0\%$ or $\geq 9.0\%$)
- Patients who are not compliant with study medication administration requirements (dose, frequency and minimum exposure etc.). This criterion includes concomitant oral antidiabetic medication (SoC). Defined as:
 - Stable dose of an oral antidiabetic agent (metformin and/or sulfonylurea [SU]) and/or insulin for at least 2 months prior to screening for the subset of patients who are not treatment naïve.
- Patients taking concomitant medications not complying with:
 - Either is not treated with or has been on a stable treatment regimen with any of the following medications for a minimum of 1 month prior to Visit 1

(Screening):

- (a) Oral contraceptives (female patients)
 - (b) Antihypertensive agents
 - (c) Lipid-lowering agents
 - (d) Thyroid replacement therapy
 - (e) Antidepressant agents
- Patients who develop withdrawal criteria during the study but were not discontinued from study medication/study.
 - Patients who do not comply with the protocol-specified assessments criteria (efficacy + safety).
 - Patients who do not adhere to the protocol-specified visit schedule.
 - Other factors, for example GCP violations, fraudulent data which will exclude patients at that level.
 - Emergency unblinding during the 24-week double-blind treatment period.
 - Discrepancies in IVRS versus electronic case report form (eCRF) randomization stratification factors.

Important protocol deviations (PDs or other underlying factors), as detailed in a separate PD plan, will be identified and documented by the study physicians and statisticians prior to unblinding of the data.

3. PRIMARY AND SECONDARY VARIABLES

3.1 Primary efficacy variable

The primary efficacy endpoint is change in HbA1c from baseline Visit 2 (Week 0) to Visit 7 (Week 24).

3.2 Secondary efficacy variables

The following are the secondary efficacy endpoints:

- Change in HbA1c from baseline Visit 2 (Week 0) to Visit 10 (Week 52), and to each intermediate visit as applicable
- Change in fasting plasma glucose concentration from baseline Visit 2 (Week 0) to Visit 7 (Week 24), Visit 10 (Week 52), and to each intermediate visit as applicable
- Proportions of patients achieving HbA1c goals of <6.5%, ≤6.5% and <7.0% at Visit 7 (Week 24), Visit 10 (Week 52), and at each intermediate visit as applicable
- Change in body weight from baseline Visit 2 (Week 0) to Visit 7 (Week 24), Visit 10 (Week 52), and to each intermediate visit as applicable

- Change in fasting insulin from baseline Visit 2 (Week 0) to Visit 7 (Week 24), Visit 10 (Week 52), and to each intermediate visit as applicable
- Change in beta-cell function (HOMA-B) and insulin sensitivity (HOMA-S) as measured by homeostasis model assessments in EQW patients not taking insulin from baseline Visit 2 (Week 0) to Visit 7 (Week 24), Visit 10 (Week 52), and to each intermediate visit as applicable
- Change in lipids (total cholesterol, high-density lipoprotein [HDL], low-density lipoprotein [LDL] and triglycerides) from baseline Visit 2 (Week 0) to Visit 5 (Week 12), Visit 7 (Week 24), Visit 10 (Week 52), and to each intermediate visit as applicable
- Change in blood pressure (systolic and diastolic) from baseline Visit 2 (Week 0) to Visit 7 (Week 24), Visit 10 (Week 52), and to each intermediate visit as applicable
- Plasma exenatide concentrations at baseline Visit 2 (Week 0), Visit 7 (Week 24), Visit 10 (Week 52), and each intermediate visit, as applicable
- Proportions of patients discontinuing the study and the proportion of patients needing rescue due to failure to maintain glycemic control, and number of rescue episodes at Visit 7 (Week 24), Visit 10 (Week 52), and at each intermediate visit as applicable

3.3 Exploratory efficacy variables

The exploratory efficacy endpoints are:

- Change in Body Mass Index (BMI) from baseline Visit 2 (Week 0) to Visit 7 (Week 24), Visit 10 (Week 52), and to each intermediate visit as applicable
- Change in body weight percentile and height percentile from baseline Visit 2 (Week 0) to Visit 7 (Week 24), Visit 10 (Week 52), and to each intermediate visit as applicable. The height and weight percentile will be determined based on the standardized growth chart for boys and girls (developed by the National Center for Health Statistics in collaboration with the National Center for Chronic Disease Prevention and Health Promotion).

3.4 Safety variables

- Corresponding to the primary safety objective, safety and tolerability endpoints including the incidence of treatment emergent AEs (TEAEs; see section 4.2.4.1), antibodies to exenatide, physical examinations, laboratory measurements (clinical, chemistry/hematology), and vital sign measurements from baseline Visit 2 (Week 0) to Visit 7 (Week 24), Visit 10 (Week 52), and to each intermediate visit as applicable
- Proportions of patients reporting different injection site reactions at Visit 3 (Week 4) through Visit 10 (Week 52) (see Section 4.2.4.2 for details of injection site reaction reporting)
- Change in calcitonin, pancreatic amylase, and lipase from baseline Visit 2 (Week 0) to Visit 5 (Week 12) and Visit 10 (Week 52)

- Change in Thyroid-stimulating hormone (TSH), thyroxine (free T4), prolactin, cortisol, insulin-like growth factor 1 (IGF-1), and Dehydroepiandrosterone (DHEAS) from baseline Visit 2 (Week 0) to Visit 5 (Week 12), Visit 7 (Week 24), and Visit 10 (Week 52)
- Tanner pubertal stage at baseline Visit 2 (Week 0), Visit 5 (Week 12), Visit 7 (Week 24), Visit 9 (Week 40), and Visit 10 (Week 52)

3.5 Exploratory safety variables

- Change in carcinoembryonic antigen (CEA) from baseline Visit 2 (Week 0) to Visit 5 (Week 12) and Visit 10 (Week 52)
- Change in bone specific alkaline phosphatase and N-telopeptide from baseline Visit 2 (Week 0) to Visit 5 (Week 12), Visit 7 (Week 24) and Visit 10 (Week 52)
- Change in follicle-stimulating hormone (FSH), luteinizing hormone (LH), FSH/LH, total testosterone, sex hormone binding globulin (SHBG), and estradiol from baseline Visit 2 (Week 0) to Visit 5 (Week 12), Visit 7 (Week 24), and Visit 10 (Week 52)
- Change in total testosterone and SHBG also at Visit 9 (Week 40). Free testosterone will be calculated from total testosterone and SHBG values at Visit 5 (Week 12), Visit 7 (Week 24), Visit 9 (Week 40), and Visit 10 (Week 52).

3.6 Definition of study variables

Refer to Section 4.3 for details on conventions such as visit windowing and handling of duplicate efficacy assessments.

3.6.1 Study baseline

The baseline measurement is defined as the last non-missing (either numerical or character) value, including values from unscheduled visits, collected on or prior to the first dose of study medication in the double-blind treatment period. Assessments carried out on the date of first dose are assumed to have been done pre-dose unless time information indicates otherwise. In case of multiple measurements for a given variable with tied collection date or date/time, the mean of the values will be calculated for baseline. If the baseline value is missing for a given variable, change from baseline will be missing.

For change from baseline summaries of data collected during the extension period, the baseline value will not be rederived.

3.6.2 Change and percent change from baseline

Change from baseline to any randomized treatment period Week t is defined as follows:

$$C_{Week\ t} = M_{Week\ t} - M_{baseline},$$

Where:

- $C_{Week\ t}$ is the change from baseline at Week t ,
- $M_{Week\ t}$ is the measurement at Week t ,

- $M_{baseline}$ is the baseline measurement.

Percent change from baseline to any randomized treatment period Week t is defined as follows:

$$P_{Week\ t} = 100 \times (M_{Week\ t} - M_{baseline}) / M_{baseline}.$$

If the baseline value is zero, the percent change will be missing.

3.6.3 Early Termination visit

If a patient discontinues after randomization but prior to completion of the study treatment period, the patient will be invited to return as soon as possible to the study site for an early termination (ET) visit. Patients will be invited to return to the study site for an ET visit to collect HbA1c, fasting plasma glucose, body weight, and clinical safety laboratory measures. Patients who discontinue study medication prior to Visit 11 (Week 62/Study Termination) will also participate in the Extended Safety Follow-up Period, unless they have a height increase of less than 5 mm over a 6-month interval at study-site visits prior to discontinuation of study medication.

3.6.4 Rescue therapy

Rescue therapy is defined as any new concomitant medication (see Section 4.2.1.4 for detail) with therapy reason given as “Protocol defined exacerbation of disease under study”.

A rescue episode will be defined as the first unique rescue therapy entry on the CM eCRF. If a patient has multiple entries on the CM form flagged as a rescue therapy, the first will be considered the point at which the patient was rescued.

Increases in insulin from baseline in patients receiving insulin at baseline will be programmatically derived from the CM CRF and reviewed by the clinical team prior to unblinding. Increases identified as potential rescue episodes will be queried at the site-level and therapy reason may be updated to “Protocol defined exacerbation of disease under study”.

For patients who require initiation of rescue therapy and continue study treatment, only data before initiation of rescue therapy will be included in the primary efficacy analysis. If HbA1c is measured before rescue therapy, then we will include the HbA1c measurement. If HbA1c is measured on the date of first rescue therapy but no time information is available to indicate if it was taken before rescue therapy, then HbA1c will be assumed to be prior and included in the primary efficacy analysis. Sensitivity analyses including data after initiation of rescue therapy will be carried out to test the robustness of the missing data assumption.

3.6.5 Study periods

The following definitions will be used to assign data to the correct study period. For details on which data will be presented in outputs for each endpoint, refer to Section 4.2.

3.6.5.1 Efficacy

Controlled assessment period: For efficacy parameters, the controlled assessment period will be defined as date of first dose of randomized study medication to date of the Week 24 visit, or the Early Termination visit for patients who discontinue the study prior to Week 24.

Extension period: For efficacy parameters, the start date of the extension period will be defined as date of first dose of open-label EQW + 1 day, in order to ensure assessments done on the Week 24 visit date are assigned to the controlled assessment period. The end date of the extension period will be defined as the Week 52 visit, or the Early Termination visit for patients who discontinue the study prior to Week 52. The extension period will only be defined for patients who enter the extension period and receive at least one dose of open-label EQW.

Treatment period: The treatment period for efficacy parameters will be defined as the controlled assessment period and extension period combined i.e. date of first dose of randomized study medication to date of Week 52 visit or Early Termination visit for patients who discontinue the study prior to Week 52.

See Section 4.1.3 for details on missing data handling.

3.6.5.2 Safety and concomitant medications

Adverse events, hypoglycemic events and concomitant medications on the date of first dose of open-label EQW (Week 24 visit) will be assigned to the extension period as this is considered a conservative approach. Other safety assessments at the Week 24 visit will be considered to have been carried out pre-dose and will therefore be assigned to the controlled assessment period. This is reflected in the definitions below.

Controlled assessment period:

- For patients who do not enter the extension period, the controlled assessment period will be defined as date of first dose of randomized study medication to date of last dose of randomized study medication + 7 days (or + 90 days after last dose of study medication for reporting of serious adverse events (SAEs) and other clinically significant or related AEs).
- For patients who go on to enter the extension period, the controlled assessment period for all safety parameters except AEs, hypoglycemic events and concomitant medications will be defined as date of first dose of randomized study medication to date of first dose of open-label EQW. For AEs, hypoglycemic events and concomitant medications, the controlled assessment period will be defined as date of first dose of randomized study medication to date of the first dose of open-label EQW – 1 day, in order for AEs, hypoglycemic events and medications recorded on the date of first dose of open-label EQW to be assigned to the extension period.

Extension period: For all safety parameters, except AEs, hypoglycemic events and concomitant medications, the extension period will be defined as date of first dose of open-

label EQW + 1 to date of last dose of open-label EQW + 7 days. For AEs, hypoglycemic events and concomitant medications, the extension period will be defined as date of first dose of open-label EQW to date of last dose of open-label EQW + 7 days (or + 90 days for SAEs and other clinically significant or related AEs). The extension period will only be defined for patients who enter the extension period and receive at least one dose of open-label EQW.

Treatment period: The treatment period for safety parameters will be defined as the controlled assessment period and the extension period combined i.e. date of first randomized study dose to the date of last dose of study medication + 7 days (randomized study medication for patients who do not enter the extension period or last dose of open-label EQW for patients who enter the extension period). For SAEs and other clinically significant or related AEs, the last dose of study medication + 90 days will be used for reporting.

See Section 4.1.3 for details on missing data handling.

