5.7 Treatment compliance

The administration of all study drugs (including investigational products) should be recorded in the appropriate sections of the CRF.

The study drug dispensation as per visits has been summarized in Table 4.

Table 4 Study Drug Dispensation per Visits Schedule

Visit (week)	Exenatide/placebo vial 4-weeks kit. (24-Week Controlled assessment Period).	Exenatide vial 4-weeks kit (28-Week Extension Period).	Diluent 4-weeks kit
Visit 2 (Week 0)	1	N/A	1
Visit 3 (Week 4±2 days)	1	N/A	1
Visit 4 (Week 8±2 days)	1	N/A	1
Visit 5 (Week 12±2 days)	2	N/A	2
Visit 6 (Week 18±2 days)	2	N/A	2
Visit 7 (Week 24±2 days)	N/A	1	1
Visit 8 (Week 28±2 days)	N/A	3	3
Visit 9 (Week 40±2 days)	N/A	3	3
Visit 10 (Week 52±2 days)	N/A	N/A	N/A

Abbreviation: N/A=not applicable

Visit 2 (Week 0): At Visit 2, a 4-week supply of blinded study medication kits will be dispensed to all patients, according to their assigned treatment group.

Visit 3 (Week 4) and Visit 4 (Week 8): At Visit 3 and Visit 4 an additional 4-week supply of study medication will be dispensed to all patients, according to their assigned treatment group.

Visit 5 (Week 12) and Visit 6 (Week 18): At Visit 5 and Visit 6 an additional 8-week supply of study medication will be dispensed to all patients, according to their assigned treatment group.

Visit 7 (Week 24): At Visit 7 a 4-week supply of open label study medication will be dispensed to all patients.

Visit 8 (Week 28) and Visit 9 (Week 40): At Visit 8 and Visit 9 a 12-week supply of open label study medication will be dispensed to all patients.

Visit 10 (Week 52/End of Treatment): Patients to return all used and unused study medication to the study site.

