Abbreviations: EQW, exenatide once weekly; P, phone call

Note: All visits scheduled during the controlled assessment period and during the open-label extension period should occur within ± 2 days of the scheduled date, relative to Visit 2 (Week 0).

Visit 11 must occur at least 10 weeks from final dose of study medication but no more than 12 weeks.

The Investigator and/or qualified study-site personnel will contact patients by phone at Week 2, Week 16, and Week 26 to discuss study compliance, address any questions related to study medication, and review adverse events.

Note: The first dose of open-label EQW during the extension period will be given at the Week 24 visit.

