4.3 Conventions

4.3.1 Visit assignments for efficacy variables

All visits scheduled during the 24-week controlled assessment and 28-week extension period should occur within ± 2 days of the scheduled date relative to Visit 2 (Week 0) per the CSP.

Patients do not always adhere strictly to the visit timing in the CSP. Therefore, the designation of visits during the treatment period will be based on the day of evaluation relative to the start of the controlled assessment period (day of study medication = Day 1) rather than the nominal visit recorded in the eCRF.

To assign a measurement to a Week t during the study, the first step is to select all measurements falling within the study period. Mutually exclusive relative day windows are used to determine the Week t measurement. These relative day windows are defined to provide derived visits that correspond to the post-baseline time points specified in the CSP. Some restrictions may exist on some laboratory assessments to be included in efficacy analyses. These restrictions will be reflected in the relative day ranges. Visit windows for efficacy variables are listed below.

Visit windows will not be used for Visit 11 (Week 62) and data will be presented per the visit label.

Table 3.1 Visit Windows: HbA1c, Body weight, BMI, Rescue medication (based on start date of medication) and blood pressure

Visit	Analysis Visit	Week	Period	Target Day	Day range
2	0	0	CAP	1	Baseline
3	1	4	CAP	29	2-42
4	2	8	CAP	57	43-70
5	3	12	CAP	85	71-105
6	4	18	CAP	127	106-147
7	5	24	CAP	minimum (last day of CAP or 169)	148 to last day of CAP

Visit	Analysis Visit	Week	Period	Target Day	Day range
8	6	28	EP	maximum (last day of CAP+1 or 197)	last day of CAP +1 to 238
9	7	40	EP	281	239-322
10	8	52	EP	minimum (last day of EP or 365)	323 to last day of EP

CAP: Controlled assessment period. EP: Extension period.

Table 3.2 Visit Windows: Fasting plasma glucose, Fasting Insulin, Plasma Exenatide

Visit	Analysis Visit	Week	Period	Target Day	Day range
2	0	0	CAP	1	Baseline
3	1	4	CAP	29	2-42
4	2	8	CAP	57	43-70
5	3	12	CAP	85	71-126
7	5	24	CAP	minimum (last day of CAP or 169)	127 to last day of CAP
10	8	52	EP	minimum (last day of EP or 365)	last day of CAP +1 to last day of EP

CAP: Controlled assessment period. EP: Extension period.

Table 3.3 Visit Windows: Fasting Lipids

Visit	Analysis Visit	Week	Period	Target Day	Day range
2	0	0	CAP	1	Baseline
5	3	12	CAP	85	2-126
7	5	24	CAP	minimum (last day of CAP or 169)	127 to last day of CAP

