4.3.3 Visit assignment for safety variables

Below tables provide day windows for vital signs, safety lab parameters (clinical chemistry/hematology), and growth and development hormones.

Table 3.5 Visit Windows: Vital signs

Visit	Analysis Visit	Week	Period	Target Day	Day range
2	0	0	CAP	1	Baseline
3	1	4	CAP	29	2-42
4	2	8	CAP	57	43-70
5	3	12	CAP	85	71-105
6	4	18	CAP	127	106-147
7	5	24	CAP	minimum (last day of CAP or 169)	148 to last day of CAP
8	6	28	EP	maximum (last day of CAP+1 or 197)	last day of CAP +1 to 238
9	7	40	EP	281	239-322
10	8	52	EP	minimum (last day of EP or 365)	323 to last day of EP

CAP: Controlled assessment period. EP: Extension period.

Table 3.6 Visit Windows: Injection site reaction

Visit	Analysis Visit	Week	Period	Day range
3	1	4	CAP	1-42
4	2	8	CAP	43-70
5	3	12	CAP	71-105
6	4	18	CAP	106-147
7	5	24	CAP	Subjects not entering EP: 148 to last day of CAP
				Subjects entering EP: 148 to last day of CAP -1
8	6	28	EP	Subjects not entering EP: last day of CAP +1 to 238
				Subjects entering EP: last day of CAP to 238
9	7	40	EP	239-322
10	8	52	EP	323 to last day of EP

CAP: Controlled assessment period. EP: Extension period.

Table 3.7 Visit Windows: Total testosterone, SHBG, Tanner Pubertal Stage

Visit	Analysis Visit	Week	Period	Target Day	Day range
2	0	0	CAP	1	Baseline
5	3	12	CAP	85	2-126
7	5	24	CAP	minimum (last day of CAP or 169)	127 to last day of CAP
9	7	40	EP	maximum (last day of CAP+1 or 281)	last day of CAP +1 to 322
10	8	52	EP	minimum (last day of EP or 365)	323- last day of EP

CAP: Controlled assessment period. EP: Extension period.

Table 3.8 Visit Windows: Laboratory (hematology, clinical chemistry, urinalysis), Growth and development hormones such as TSH, FSH etc., Bone specific Alkaline phosphatase and N-telopeptide.

Visit	Analysis Visit	Week	Period	Target Day	Day range
2	0	0	CAP	1	Baseline
5	3	12	CAP	85	71-126
7	5	24	CAP	minimum (last day of CAP or 169)	127 to last day of CAP
10	8	52	EP	minimum (last day of EP or 365)	last day of CAP +1 to last day of EP

CAP: Controlled assessment period. EP: Extension period.

Table 3.9 Visit Windows: calcitonin, pancreatic amylase, lipase, CEA

Visit	Analysis Visit	Week	Period	Target Day	Day range
2	0	0	CAP	1	Baseline
5	3	12	CAP	minimum (last day of CAP or 85)	71 to last day of CAP
10	8	52	EP	minimum (last day of EP or 365)	last day of CAP +1 to last day of EP

CAP: Controlled assessment period. EP: Extension period.

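### The SAP ends the extension period for non-AE safety data 7 days after the last dose, which on the supply schedule leaves no slack for a permitted Week 52 visit

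*SAP*

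**What the plan says.** **Period definition.** For all safety parameters except adverse events, hypoglycemic events and concomitant medications, SAP 3.6.5.2 gives the extension period (EP) as "label EQW + 1 to date of last dose of open-label EQW + 7 days", that is, from the day after the first open-label dose to 7 days after the last. The Treatment period at the end of the same section also stops at last dose + 7 days.

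**Visit windows.** In SAP 4.3.3, the Week 52 row of Tables 3.8 and 3.9 is "last day of CAP +1 to last day of EP". In Tables 3.5 and 3.7 it runs from Day 323 to the same last day of EP. SAP 4.3.1 allows visits within 2 days either side of the "scheduled date relative to Visit 2 (Week 0) per the CSP". It assigns data by study day and not by the recorded visit, and presents Week 62 by visit label only.

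**Efficacy, for contrast.** SAP 3.6.5.1: "The end date of the extension period will be defined as the Week 52 visit".

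**Dosing and supply.** SAP 1.2: "The first dose of open-label EQW during the extension period will be given at the Week 24 visit". Protocol 5.7: "At Visit 7 a 4-week supply of open label study medication will be dispensed to all patients", and "At Visit 8 and Visit 9 a 12-week supply of open label study medication will be dispensed to all patients". Table 4 dispenses nothing at Visit 10, where the instruction is "Patients to return all used and unused study medication to the study site". The Visit 10 list in Protocol 6.2.3.10 contains no dispensing or administration; the list for Visits 8 and 9 in 6.2.3.9 contains both.

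**Contrary text.** The protocol synopsis, Protocol 3.1 and SAP 1.2 place the last dose at Visit 10 (Week 52). Protocol 3.1 also describes Group B as treated through Week 52.

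**The concern.** Week 52 is a scheduled end-of-treatment visit, and SAP 3.6.5.5 uses a Week 52 assessment to define an extension treatment completer. Yet the safety period is tied to the last injection. If that injection is one week before the visit, the period ends on the nominal visit day, and ordinary timing within the protocol's own tolerances can push the Week 52 sample past the end. No rule recovers it: the recorded visit label is not used, and the Week 62 summary takes only data labelled Week 62.

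Under Tables 3.8 and 3.9, Week 52 is the only extension time point for hematology, chemistry, urinalysis, the growth and development hormones, bone markers, calcitonin, amylase, lipase and CEA. Under Tables 3.5 and 3.7 it is the last one for vital signs, total testosterone, SHBG and Tanner stage. Safety over about one year is a stated secondary objective, and only about 77 patients are randomized. There is also an internal mismatch. Blood pressure appears in efficacy Table 3.1 and in safety Table 3.5, so the same Week 52 reading could be counted in one and excluded from the other.

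**Working it through.** **Inputs**
- EP end for these data: last open-label dose + 7 days (SAP 3.6.5.2).
- First open-label dose: Week 24 visit (SAP 1.2).
- Open-label kits: 1 at Week 24, 3 at Week 28, 3 at Week 40, none at Week 52 (Protocol Table 4); 4 doses per kit (Protocol 5.5.1).
- Visit tolerance: 2 days either side (SAP 4.3.1). Dose tolerance: 2 days either side (Protocol 5.5.2).

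**Reproducing the SAP's target days.** Study day = 1 + 7 × week. Weeks 4, 24, 28, 40 and 52 give Days 29, 169, 197, 281 and 365, which match the SAP tables.

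**Last supplied dose.** 4 × (1 + 3 + 3) = 28 weekly doses. Starting at Week 24, the last is Week 24 + 27 = Week 51, and 1 + 7 × 51 = Day 358.

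**Nominal EP end.** 358 + 7 = Day 365. The permitted Visit 10 days are 363 to 367. With the last dose on schedule, Days 366 and 367 fall outside: 2 of 5.

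**Both tolerances together.** The last dose is on Day 356 to 360. A visit is inside if visit day ≤ last dose day + 7.

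| Last dose day | EP ends | Permitted visit days outside | Count |
|---|---|---|---|
| 356 | 363 | 364–367 | 4 of 5 |
| 357 | 364 | 365–367 | 3 of 5 |
| 358 | 365 | 366–367 | 2 of 5 |
| 359 | 366 | 367 | 1 of 5 |
| 360 | 367 | none | 0 of 5 |

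Total outside: 4 + 3 + 2 + 1 + 0 = 10 of 25, by 1 to 4 days.

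**Week 51 dose missed.** The last dose is Week 50, Day 351 (range 349 to 353). The EP ends on Day 358 (range 356 to 360), before the earliest permitted visit on Day 363, so all 25 combinations fall outside.

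**Dose given at Week 52 instead.** The last dose is on Day 363 to 367 and the EP ends on Day 370 to 374, so 0 of 25 fall outside.

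**Exposure categories (SAP 4.2.2).** The top category starts at 364 days. A Week 51 last dose gives 358 − 1 + 7 = 364, and a Week 52 last dose gives 365 − 1 + 7 = 371. Both fall in it, so it does not settle which reading applies.

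**With the fix.** If the EP ends at the later of last dose + 7 days and the Week 52 visit date, 0 of 25 fall outside under either dosing reading.

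**The case against.** **The last dose may be at Week 52.** Three passages say so, and if it is given, completers who take it lose nothing. This stands. Table 4 and the Visit 10 procedures point the other way. The drug-administration row of Protocol Table 1 could not be read with confidence and is given no weight here. The documents contradict themselves and must be reconciled.

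**The 7-day rule is deliberate.** The SAP's amendment history says the windows were aligned so that completers and early discontinuers are treated alike, and the 7-day margin is used throughout for on-treatment events. That is a sound reason for adverse events. It does not answer the problem for a scheduled assessment: the rule can exclude the very visit that defines a completer and that the efficacy period keeps.

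**The size is easily overread.** A reader might infer that 40% of compliant patients lose their Week 52 safety data. The documents give no distribution of dose or visit days. A patient seen exactly 7 days after the last dose is retained; only those seen 8 or more days after it are affected.

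**The data do not disappear.** A reader might also infer that the values go unreported. Laboratory listings include all scheduled and unscheduled results (SAP 4.2.4.4), and the potential Hy's law count extends to follow-up (SAP 4.2.4.3). Chemistry, hematology, urinalysis, calcitonin and vital signs are repeated at Visit 11 (Protocol 6.2.3.11). That list does not include amylase, lipase, CEA, the hormones, bone markers or Tanner stage.

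**Week 24.** It is tempting to say the controlled period has the same supply limit. It does not: 1 + 1 + 1 + 2 + 2 = 7 kits give 28 doses for 24 weeks. The last-dose + 7 rule does apply to patients who do not enter the extension, but the protocol has all patients entering, so this group should be small.

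**Conclusion.** The concern holds conditionally. On the reading given by Table 4 and the Visit 10 procedures, the safety extension period ends on Day 365 for a patient dosed on schedule. A permitted Visit 10 on Day 366 or 367, or any visit 8 or more days after the last dose, then falls out of the Week 52 by-visit safety summaries and the extension shift tables. This affects 10 of 25 permitted day combinations, and all 25 if the Week 51 dose is missed. On the reading that places a dose at Visit 10, it affects none for completers who take that dose.

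The consequence is confined to those summaries and shift tables. The counts describe permitted combinations and support no estimate of how many patients would be affected. The finding rests on the Week 52 windows being capped by the safety definition of the EP. It does not need the period filter in SAP 4.3.1, which sits under an efficacy heading. The SAP should be amended, because the rule as written can alter what the Week 52 safety tables contain and the correction works under either dosing reading.

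**What to change.** 1. In SAP 3.6.5.2, for scheduled safety assessments other than adverse events, hypoglycemic events and medications, end the extension period at the later of last open-label dose + 7 days and the Week 52 visit date for extension treatment completers as defined in 3.6.5.5.
2. Make the same change to the safety Treatment period in that section; otherwise the extension period could run past the period that contains it.
3. Apply the same wording, with last randomized dose + 7 days and the Week 24 visit date, to controlled-period treatment completers who do not enter the extension.
4. Leave the windows for adverse events, hypoglycemia and medications as they are. Tables 3.5 and 3.7 to 3.9 need no edit, because they refer to the last day of EP.
5. Separately, reconcile the passages placing the last dose at Visit 10 with Table 4 and the Visit 10 procedure list. The period change need not wait for this.

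The cost is a few sentences in one SAP section and a small change to the period derivation. The downside is that a few Week 52 values will have been taken slightly more than 7 days after the last dose; a table footnote can say so.
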